### 7.3.2 6-Hour Visit (Visit 2)

- The subject will be asked to score their subjective response as detailed in CVI Grading scales.

[REDACTED]

- [REDACTED]
- [REDACTED]
- [REDACTED]
  - [REDACTED]
  - [REDACTED]
  - [REDACTED]
  - [REDACTED]
  - [REDACTED]
  - [REDACTED]
  - [REDACTED]
  - [REDACTED]
- Lens fit (OD/OS) will then be assessed and graded according to the CVI grading scales (Appendix 2). [REDACTED]
  - Lens centration (mm)
  - Post-blink movement (mm)
  - Upgaze lens lag (mm)
  - Horizontal lens lag/mobility rating (0-4)
  - Lens tightness (%)
  - Lens movement characteristics (slow, medium, fast)
  - Overall lens fit acceptance (0-4 scale) and investigator reason, if unacceptable.
- The lenses will be removed by the subject and their subjective responses for ease of lens removal (0-100 scale) (OD/OS) will be recorded. The lenses will be retained for return to the Sponsor.
- Slit lamp biomicroscopy will be assessed according to the guidelines set out in CVI Grading scales.
- The subject will be discharged and will sign the exit statement.

### 7.3.3 Summary of Visits and Procedures

Table 2 summarizes the visits and procedures for the study.

**Table 2: Summary of Visits and Procedures**

	Visit 0 Screening / Baseline	Visit 1 Dispense	Visit 2 6-hour follow-up & Exit
Informed consent	✓	-	-
Meet inclusion/exclusion criteria	✓	-	-
History at baseline	✓	-	-
Demographics	✓	-	-
HVID / palpebral aperture size	✓	-	-
Auto-refraction & keratomtery	✓	-	-
Sphero-cylindrical refraction	✓	-	-
HIHC & HILC VAs with spectacle refraction	✓	-	-
Slit-lamp biomicroscopy	✓	-	✓
	-	✓	-
	-	✓	✓
	-	✓	✓
Lens fit assessments	-	✓	✓
	-	✓	-
	-	✓	✓
Exit VAs	-	-	✓
Study Exit	-	-	✓

## 8 Adverse Event Reporting

### 8.1 Adverse Event Definitions

An 'adverse event' refers to any undesirable clinical occurrence in a participant, whether it is considered to be device-related or not. Adverse events (AE) may be classified as 'unanticipated adverse device effects,' 'serious adverse events,' 'significant adverse events,' or 'non-significant adverse events,' as defined below.

Classification	Definition
Serious Adverse Event	Those events that are life-threatening, or result in permanent impairment of a body function, or permanent damage to a body structure or necessitate medical (therapeutic) or surgical intervention to preclude permanent impairment of a body function or permanent damage to a body structure.
Significant Adverse Event	Those non-serious adverse events that occur with contact lens usage that are not sight-threatening but are usually symptomatic and may warrant therapeutic management and /or temporary or permanent discontinuation of contact lens wear.
Non-Significant Adverse Events	Those less severe non-serious adverse events that occur with contact lens usage that are not sight-threatening, may or may not be symptomatic and may warrant palliative management, such as ocular lubricants or temporary interruption of contact lens wear.
Unanticipated Adverse Device Effect	Adverse events in a clinical trial that were not previously identified in the protocol in terms of nature, severity, or degree of incidence. An Unanticipated Serious Adverse Device Effect is an unanticipated adverse event that is serious in nature and caused by or associated with the device and is considered reportable.

AE classification, coding (for reporting to the sponsor) and examples are provided in the following table of Contact Lens Adverse Event Classification and Reporting table:

Code	Condition	Reporting
Serious Adverse Events		
01	Presumed infectious keratitis or infectious corneal ulcer	Notify sponsor as soon as possible, within 24 hours ; IRB reporting as per requirements
02	Permanent loss of $\geq 2$ lines of best spectacle corrected visual acuity (BSCVA)	
03	Corneal injury that results in permanent opacification within central cornea (6mm)	
04	Uveitis or Iritis (e.g. presence of anterior segment inflammation as described in ISO 11980, Annex B)	
05	Endophthalmitis	
06	Hyphema	
07	Hypopyon	
08	Neovascularization within the central 6mm of cornea	
00	Other serious event	
Significant Adverse Events		
11	Peripheral (outside central 6mm), non-progressive, non-infectious ulcer	Notify sponsor as soon as possible, within 5 working days ; IRB reporting as per requirements
12	Symptomatic corneal infiltrative event	
13	Superior epithelial arcuate lesions (SEALs) involving epithelial split	
14	Corneal staining $\geq$ dense coalescent staining up to 2mm in diameter (e.g. moderate, ISO 11980 grade 3)	
15	Corneal neovascularization $\geq 1.0$ mm vessel penetration (e.g. $\geq$ ISO 111980 Grade 2), if 2 grade change from baseline	
16	Any temporary loss of $\geq 2$ lines BSCVA for $\geq 2$ wks	
17	Any sign and/or symptom for which subject is administered therapeutic treatment or which necessitates discontinuation of lens wear for $\geq 2$ weeks	
10	Other significant event	
Non-significant Adverse Events		
21	Conjunctivitis (bacterial, viral or allergic)	Notify sponsor as

**Confidential**

13

22	Papillary conjunctivitis if $\geq$ mild scattered papillae/follicles approximately 1mm in diameter (e.g. ISO 11890 Grade 2), if 2 grade change from baseline	soon as possible, within 5 working days ; IRB reporting as per requirements
23	Asymptomatic corneal infiltrative events	
24	Any sign and/or symptom for which temporary lens discontinuation for > 1 day is recommended (if not already classified)	
20	Other sign and/or symptom warranting classification as a non-significant adverse event	

### Normal or adaptive symptoms

Transient symptoms such as end-of-day dryness, lens awareness, itching or burning or other discomfort may occur with contact lens wear and may occasionally reduce wearing time. **These are not reported as adverse events unless in the investigator's opinion they are unexpected in nature, severe or have a high rate of occurrence.**

This clinical study will also ascertain satisfaction or preference with subjective attributes such as comfort, vision, or lens handling. Responses to these subjective questionnaires will not be considered as Adverse Events.

## 8.2 Procedures for Adverse Events

---

Treatment of an adverse event will depend on its nature and severity. Based on the clinical judgment of the investigator the subject may be referred to an ophthalmologist for treatment. The investigator will attempt to determine whether the reaction is related to the test device or a result of other factors. An Adverse Event Form will be completed for each adverse event. If both eyes are involved, a separate Adverse Event Form will be completed *for each eye*. Whenever possible, the adverse event will be photo-documented.

Expenses incurred for medical treatment as part of study participation will be paid by the sponsor (bills and prescription receipts kept). The subject must be followed until resolution and a written report completed indicating the subsequent treatment and resolution of the condition.

## 8.3 Reporting Adverse Events

---

All potential Serious and Unanticipated Adverse Device Effects that are related or possibly related to subject participation will be reported to the Principal Investigator and the sponsor within 24 hours of the investigator becoming aware of the event. The Principal Investigator will report the event to the IRB as soon as possible (by fax, mail/delivery, phone, or email). All fatal or life threatening events will be reported immediately to the IRB.

Significant and Non-Significant Adverse Events will be reported to the sponsor as soon as possible, but no later than 5 working days after the occurrence.

[figure not shown]
Sponsor contact details are:

Contact:

Email:

Phone:

Address:

## 8.4 Discontinuation from the Study

---

A subject's study participation may be discontinued at any time if, in the opinion of the sponsor or the investigator it is in the best interest of the subject. All discontinuations will be fully documented on the appropriate study forms and the Discontinuation Form will be completed.

## 9 Device Malfunctions

---

A device malfunction means the failure of the device to meet its performance specification or otherwise perform as intended. *Any defective lens that is likely to cause or contribute to a Serious Adverse Event should be reported to the Principal Investigator and the sponsor **within 24 hours** of the investigator becoming aware of the malfunction.*

Other defective lenses should be reported to the Sponsor as soon as possible.

This clinical study will also ascertain satisfaction or preference with subjective attributes such as comfort, vision, or lens handling. Responses to these subjective questionnaires will not be considered as complaints or Device Malfunctions.

## **10 Statistical Analysis**

---

### **10.1 Statistical analysis**

---

Summary statistics will be produced (e.g. mean, standard deviation). Paired t test will be used to compare slit lamp biomicroscopy, lens fit and subjective scores between study lens types. Repeated Measures Analysis of Variance (ANOVA) or paired analysis will be used to compare the variables between study visits. The critical alpha level for statistical significance will be set at  $p \leq 0.05$ , with adjustment for multiple comparisons.

All participants who were evaluated will be used in the analysis. In the event of missing data, individual data points will be excluded in the analysis and not extrapolated from the collected data.

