## 2 Study Objective

---

The purpose of this study is to validate the clinical performance of [REDACTED] lenses when worn over a period of 6 hours of wear.

The primary variable of interest is:

- Lens fit and lens fit preference

Additional variable of interest are:

- [REDACTED]
- [REDACTED]
- [REDACTED]
- [REDACTED]
- [REDACTED]

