### 2.1 Study Hypothesis

---

The study hypothesis is that the [REDACTED] contact lenses will be clinically equivalent to the Focus Dailies All Day Comfort contact lenses.

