### 7.1 Participants

---

Approx. 30 subjects [REDACTED] will be recruited for this study. Each subject will be given a unique ID number. ID numbers will not be reused in event of screen failure or discontinuation. All subjects must meet the study inclusion and exclusion criteria listed below.

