#### **Dispensing (Visit 1)**

- Baseline auto-keratometry if not done within the previous 6 months.
- HVID (mm) and palpebral aperture size (mm) measurements using slit lamp oculars.
- The study pair of contact lenses will be selected according to the randomization table (Appendix 1).
- The contact lenses will be provided by a study coordinator/technician to maintain masking of the investigator. The lenses will be inserted by the subject from the blister pack after the label is removed by the study coordinator/technician.
- [REDACTED]
  - [REDACTED]
  - [REDACTED]

- The lenses will be allowed to settle for 5 minutes.
- An initial fit assessment will be made to ensure lens fit is acceptable. The subject should be discontinued and exited if either lens fit is found unacceptable, and the primary reason for poor fit recorded.
- Monocular spherical over-refraction (SOR) will be conducted to determine if a different lens power is required.
- Final lenses will be inserted and allowed to settle for another 5 minutes, if applicable.
- The subject will be asked to give subjective ratings after settling on:

[REDACTED]

- [REDACTED]
- [REDACTED]

- [REDACTED]
- [REDACTED]
- [REDACTED]
- [REDACTED]
- [REDACTED]
- [REDACTED]
- [REDACTED]
- [REDACTED]

- Lens fit will be assessed and graded according to the CVI grading scales (Appendix 2).

[REDACTED]

- Lens centration (mm)
- Post-blink movement (mm)
- Primary gaze lag (mm)
- Upgaze lens lag (mm)
- Horizontal lens lag/mobility rating (0-4)
- Lens tightness (%)
- Lens movement characteristics (slow, medium, fast)
- Overall lens fit acceptance (0-4 scale) and investigator reason, if unacceptable.
- The subject will be discharged and asked to return for a follow-up visit after 6 hours.

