### **11.1 Study monitoring**

---

No monitoring will be required for this short feasibility study.

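### The study hypothesis is clinical equivalence, but the lenses are compared only by a paired t test for a difference, with no margin or confidence-interval rule

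*Combined protocol and SAP*

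**What the plan says.** Section 2.1 states one hypothesis: that the test lenses "contact lenses will be clinically equivalent to the Focus Dailies All Day Comfort contact lenses". Section 2 opens with "The purpose of this study is to validate the clinical performance of" the test lens, and gives the primary variable as "Lens fit and lens fit preference".

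For the comparison of lenses, Section 10.1 says "Paired t test will be used to compare slit lamp biomicroscopy, lens fit and subjective scores between study lens types". The next sentence, on repeated-measures ANOVA or paired analysis, concerns comparisons between visits. Significance is set at p ≤ 0.05 "with adjustment for multiple comparisons", without naming the method or the family of tests. Missing data points are left out.

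Section 7.1 plans "Approx. 30 subjects". Section 3 makes the design contralateral, so each subject supplies one test-control pair. Section 11.1 adds "No monitoring will be required for this short feasibility study".

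**The concern.** A paired t test asks whether the mean difference is zero. A significant result speaks against equality, and a non-significant one says only that the data did not exclude zero. Section 10.1 does not say that non-significance will be read as equivalence, but it offers no other route to that conclusion.

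If non-significance is read that way, the incentives run backwards: fewer evaluable pairs, noisier measurement or a stricter multiplicity adjustment all make equivalence easier to declare. An unspecified adjustment that covers the between-lens tests would work in this direction.

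The hypothesis also has no single quantity to attach to. The Visit 1 fit list in Section 7.3.1 holds eight items: four in mm, one percentage, two 0-4 ratings, and "Lens movement characteristics (slow, medium, fast"), which is a category that a t test on raw scores does not suit. Fit preference comes on top. No item or time point is singled out, so even a stated margin could not be applied without ambiguity.

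At stake is whether a report can say that the lenses are equivalent on evidence that would often look the same if they differed moderately.

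**Working it through.** **Side by side.** Section 2.1 needs a statement that the difference is small enough. Section 10.1 supplies a test of whether it is exactly zero. Section 10.1 shows no redaction, and the table of contents lists nothing else under Section 10. There is no power calculation to reproduce.

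**Inputs for the illustration.** From the documents: about 30 subjects, one pair each, alpha 0.05. Assumed: a two-sided test, 30 evaluable pairs, one continuous and roughly normal item, and differences and margins in SDs of the paired difference. Where a multiplicity adjustment is shown, it is Bonferroni over the eight Visit 1 fit items.

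**1. Chance of a non-significant t test.** With true difference d, the statistic is noncentral t with 29 df and noncentrality d√30. The chance is P(|T| < t(0.975, 29)) with critical value 2.045, or 2.949 at alpha 0.05/8.

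| True difference (SD) | Noncentrality | Unadjusted | Bonferroni over 8 |
|---|---|---|---|
| 0.3 | 1.64 | 64% | 88% |
| 0.4 | 2.19 | 44% | 75% |
| 0.5 | 2.74 | 25% | 57% |
| 0.8 | 4.38 | 1% | 9% |

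Fewer pairs raise the chance: at 0.5 SD (unadjusted) it is 25% with 30 pairs, 44% with 20 and 71% with 10.

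**2. An equivalence rule on the same data.** With margin M, conclude equivalence if |mean difference| + t(0.95, 29) × S/√30 < M. When S equals the true SD, the half-width is 1.699/√30 = 0.310 SD. The chance of passing is found by integrating over the chi-square distribution of S².

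| Margin (SD) | Passes if true difference = margin | Passes if true difference = 0 | Pairs for 80% power at 0 |
|---|---|---|---|
| 0.3 | 1.5% | 5% | 97 |
| 0.4 | 4.6% | 38% | 55 |
| 0.5 | 5.0% | 70% | 36 |
| 0.55 | not needed here | 81% | 30 |

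The second column is the error control that the plan lacks. It compares with 64%, 44% and 25% non-significant t tests at the first three differences. At 0.55 SD, power falls to 74% with 27 pairs and 67% with 24 (10% and 20% loss, assumed).

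**3. Identical lenses and a non-significant t test.** In 1,000,000 simulated trials, the 90% CI still reached beyond a margin of 0.3, 0.4, 0.5 or 0.55 SD in 94%, 60%, 27% and 16% of the non-significant ones. So non-significance does not establish equivalence even when equivalence is true.

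**4. Requiring several items to pass.** At 0.55 SD, independent items give 0.805^8 = 0.18 for eight items and 0.805^4 = 0.42 for four. Simulation with correlation 0.5 gives about 30% and 50%. Four is the number of continuous items listed at both visits: centration, post-blink movement, upgaze lag and tightness. The eight-item figure treats the ratings and the category as continuous, so it is only a rough guide.

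**The case against.** The fairest reply is that the analysis is incomplete but not unusable: the paired data behind the t test also yield the confidence interval that is needed, and the plan never says that a non-significant result means equivalence. Both points are true, and they make the repair cheap. They do not supply the missing decision rule.

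Second, not everything is visible. Parts of Sections 2, 7.1 and 7.3 are redacted, Appendix 2 shows no content, and Section 4.2 refers to a Master Protocol that is not in hand. A margin in one of those places cannot be wholly excluded. But Section 10.1 is unredacted and refers to no such rule.

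Third, non-significance is not empty of information. Unadjusted, it occurs in 95% of trials when the lenses are identical but only about 1% at 0.8 SD, so it does argue against large differences. It says little about small or moderate ones.

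Fourth, the study is called a short feasibility study, for which estimation alone would be reasonable. That stands as a reason to consider dropping the claim. The label appears in the monitoring section, though, and does not withdraw Section 2.1, and Section 2 describes validation.

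Finally, the overall fit rating (0-4) is arguably the closest single summary of fit, and subjects exited at the initial fit check would be absent from later fit comparisons, which favours equivalence. Both are fair points for the sponsor to settle when the primary measure is defined.

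**Conclusion.** The concern holds, and it must be fixed before the study is analysed. Followed exactly, Section 10.1 cannot confirm the only hypothesis in Section 2.1. That conclusion comes from the text and needs none of the illustrative numbers.

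The percentages rest on an assumed 30 evaluable pairs and on margins in SD units that the documents do not give. The 0.55 SD margin is simply the value at which 30 pairs reach about 80% power at zero true difference; it has no clinical basis in the documents. Whether about 30 subjects can support an equivalence claim depends on a margin that has not been stated.

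**What to change.** **Option A, keep the claim.** In Section 10.1:
- Name one lens-fit measure and one time point as primary. A continuous item listed at both visits (centration, post-blink movement, upgaze lag or tightness) is simplest. If the sponsor prefers the overall 0-4 rating, the margin and method must suit that scale.
- Have the sponsor fix and justify the margin before unmasking. Conclude equivalence only if the 90% CI of the mean paired difference (test minus control) lies wholly within plus or minus that margin.
- State the expected SD of the paired difference and the power at about 30 subjects.
- Treat the other items as secondary: paired differences with 95% CIs for continuous items, a paired rank method for 0-4 ratings, a paired categorical summary for movement speed, and the proportion preferring each lens with an exact 95% CI.
- State that a non-significant t test is not evidence of equivalence, and say which tests the multiplicity adjustment covers and by what method.
- Report, by lens, the subjects exited for unacceptable fit at the initial check, and say how they count.

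**Option B, drop the claim.** If no margin can be set, or it is too tight for about 30 subjects, reword Section 2.1 as estimating the paired differences with 95% CIs.

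**Cost.** Wording changes, plus one sponsor decision on measure and margin under Option A. No extra visits or measurements. No extra subjects are needed for 80% power if there is one primary measure, 30 evaluable pairs and a margin of about 0.55 SD or wider. Tighter margins need 36 (0.5 SD), 55 (0.4 SD) or 97 (0.3 SD) evaluable pairs. The price is that the equivalence claim becomes harder to make, or is given up.

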## 3 Study Design

---

This will be a non-dispensing, randomized, double-masked, contralateral study comparing [REDACTED] test lens against a FDADC control lens. Subjects will be randomized to wear the test lens in one eye and the control lens in the other. It is anticipated that this study will involve up to 2 scheduled visits, at Baseline (BL) and 6 hours.

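### Does naming only the paired t test leave the slow/medium/fast movement item and lens fit preference without a usable between-lens analysis?

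*Combined protocol and SAP*

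**What the plan says.** Section 2 gives the primary variable as "Lens fit and lens fit preference". Section 3 sets up the pairing: "Subjects will be randomized to wear the test lens in one eye and the control lens in the other". Section 7.1 plans about 30 subjects.

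Section 10.1 assigns one method to lens comparisons: "Paired t test will be used to compare slit lamp biomicroscopy, lens fit and subjective scores between study lens types". The sentence after it, "Repeated Measures Analysis of Variance (ANOVA) or paired analysis will be used to compare the variables between study visits", concerns visits and adds nothing for lenses. The section also promises summary statistics, with the mean and standard deviation as examples, and a 0.05 significance level "with adjustment for multiple comparisons", without naming the adjustment.

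The fit items in section 7.3 number eight at dispensing and seven at 6 hours. Most are in millimetres, in percent or on a 0-4 scale, for example "Overall lens fit acceptance (0-4 scale) and investigator reason, if unacceptable". One item at each visit, lens movement characteristics, has three verbal categories: slow, medium and fast. Both visits refer to the grading scales in Appendix 2, of which only the heading is visible. Section 10.1 does not mention preference, and the visible text does not show how fit preference is recorded. Several items in sections 2 and 7.3 and in Table 2 are redacted.

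**The concern.** A paired t test needs a number for each eye. For a slow/medium/fast item the numbers are codes, the result depends on their spacing, and shifts towards slow in some eyes and fast in others cancel in the mean. A test lens that moved less consistently than the control could therefore show no mean difference. Under the equivalence hypothesis of section 2.1, a reader might take that as similarity.

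Preference raises a different question. If each subject names one preferred lens, there is one answer per person and no pair of values to subtract. Section 10.1 then names no between-lens method for something listed within the primary variable, and it gives no rule for subjects with no preference. Two analysts might report different results from the same data.

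**Working it through.** The plan states no power, effect size or standard deviation for these items, so there is no figure of its own to reproduce. All distributions below are assumptions, with 30 pairs (section 7.1) and a two-sided 0.05 level (section 10.1 does not state sidedness).

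**1. Movement: t test against an exact symmetry test.** Simulation of 20,000 trials, codes 1-2-3, with slow/medium/fast percentages for control and test:

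| Scenario | Control | Test | t test | Exact symmetry |
|---|---|---|---|---|
| Two-way shift | 10/80/10 | 25/50/25 | 4.1% | 77.2% |
| Milder two-way shift | 10/80/10 | 21/58/21 | 4.4% | 47.4% |
| Consistent one-step shift | 27/60/13 | 13/60/27 | 66.4% | 52.6% |
| No difference, 20% of pairs discordant | same | same | 4.5% | 1.1% |

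The exact test gains much in the first two rows and loses 66.4 - 52.6 = 13.8 points in the third. The last row shows that the t test does not exceed its nominal level.

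The adjustment is not named. If it were Bonferroni over the 8 + 7 = 15 fit items, the level would be 0.05/15 = 0.0033. The t test and exact test would then have 0.3% and 24.4% in the first row, 0.3% and 5.5% in the second, and 29.0% and 12.3% in the third.

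**2. Movement: what the planned summaries show.** On codes 1-2-3 with a mean of 2, the variance equals the share of slow plus the share of fast.
- Control 10/80/10: SD = √(0.10 + 0.10) = 0.45.
- Test 25/50/25: SD = √(0.25 + 0.25) = 0.71.
- Test 21/58/21: SD = √(0.21 + 0.21) = 0.65.

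The mean hides the two-way shift. The standard deviation, which section 10.1 gives as an example summary, shows it, though without a formal test.

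**3. Movement: code spacing.** Take 30 medium control eyes against 8 slow, 19 medium and 3 fast test eyes, with t = mean difference/(SD/√30):
- Codes 1-2-3: mean -5/30 = -0.167, SD 0.592, t = -1.54, p = 0.13.
- Codes 1-2-4: mean -2/30 = -0.067, SD 0.828, t = -0.44, p = 0.66.
- Codes 1-3-4: mean -13/30 = -0.433, SD 1.006, t = -2.36, p = 0.025.

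The spread is real, but it requires someone to choose unequal codes. Nothing visible suggests that, and Appendix 2 may fix the codes.

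**4. Preference as a single choice.** Code a choice of test as +1 and of control as -1. With k of n for one lens, the mean is m = (2k - n)/n, SD = √[n(1 - m²)/(n - 1)] and t = m√n/SD.

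| Deciders | Majority | t (critical value) | t test p | Exact binomial p |
|---|---|---|---|---|
| 30 | 21 | 2.35 (2.045) | 0.026 | 0.043 |
| 30 | 20 | 1.90 (2.045) | 0.067 | 0.099 |
| 24 | 18 | 2.77 (2.069) | 0.011 | 0.023 |
| 24 | 17 | 2.20 (2.069) | 0.038 | 0.064 |
| 20 | 15 | 2.52 (2.093) | 0.021 | 0.041 |
| 20 | 14 | 1.90 (2.093) | 0.072 | 0.115 |

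At 0.05 the two methods need the same majority with 30 and with 20 deciders and differ by one subject with 24. Where the cut-offs agree, so does the power: with 30 deciders, 59% if the true share is 70% and 80% if it is 75%.

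**The case for a change.** The strongest case for a change is that both items belong to the primary variable, the lens comparison has only one named method, and two or three sentences would settle the matter with no new data. The coding of movement and the handling of no-preference answers could otherwise be chosen after the results are seen. Under an equivalence hypothesis, a missed two-way shift also errs towards the sponsor's desired conclusion.

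The reading of section 10.1 stands: it names no other between-lens method, and a comparison of means can miss a symmetric spread. The rest carries less weight. Missing a symmetric spread is not peculiar to the t test, because a sign test also cancels opposite shifts. Looking for spread rather than direction on this item is a choice of target that the visible text does not make. Post-blink movement, lag and tightness also describe how the lens moves, and overall acceptance is graded with a reason if unacceptable. A cross-tabulation of the three grades for the two eyes is compatible with the promised summary statistics and needs no amendment.

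On preference, the argument depends on a format that may sit in redacted text. If preference is graded for each eye, the paired t test covers it. If it is a single choice, a binomial or sign-type analysis with the no-preference count is the ordinary approach. A further difference test would not demonstrate equivalence in either case; that question is separate from this one.

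**Conclusion.** No change to the plan follows. The movement item is a trade-off: the exact symmetry test gains 43 to 73 points of power for the assumed two-way shifts (47.4 - 4.4 and 77.2 - 4.1), at a cost of about 14 points for a consistent one-step shift. The t test's error rate stays within 5% on equally spaced codes in the null case tried. The item is one of eight fit measures at dispensing and one of seven at 6 hours. For preference, section 10.1 lacks detail only if the answer is a single choice, and the obvious methods then differ by at most one subject at the three decider counts checked.

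This rests on equally spaced movement codes, about 30 pairs, two-sided testing and the assumed distributions. The t-test and binomial cut-offs were compared only at an unadjusted 0.05. If Appendix 2 prescribed unequal movement codes, the dependence on spacing would deserve a second look.

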#### 7.2.1 Contact lens

Subjects will be randomized to wear the Test lens in one eye and the Control lens in the other as an unmatched pair, per a predetermined randomization schedule. Subjects will be fitted with the

lens power closest to their refractive requirement. Details of the contact lenses are shown in Table 1.

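### Minor, cheap improvement: the between-lens paired t test in section 10.1 is valid but does not use the randomized eye (OD/OS)

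*Combined protocol and SAP*

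**What the plan says.** Section 10.1 gives one method for comparing the lenses: "Paired t test will be used to compare slit lamp biomicroscopy, lens fit and subjective scores between study lens types". No eye term and no baseline covariate is named. The repeated measures or paired analysis in the same section compares visits, not lenses.

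The eye is the randomized factor. Section 7.2.1 states: "Subjects will be randomized to wear the Test lens in one eye and the Control lens in the other". The schedule is described there as predetermined, and the Visit 1 instructions place the table in Appendix 1, whose content does not appear in the public copy. Section 7.3.2 records lens fit by eye.

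The primary variable in section 2 is "Lens fit and lens fit preference". Section 2.1 hypothesizes that the test "contact lenses will be clinically equivalent to the Focus Dailies All Day Comfort contact lenses". Section 7.1 plans about 30 subjects.

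Slit lamp is scheduled at Visit 0 and at 6 hours (sections 7.3.1 and 7.3.2, Table 2). Lens fit is assessed only after insertion, so it has no pre-lens value.

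Three statements affect the split that reaches the analysis. At Visit 1, "The subject should be discontinued and exited if either lens fit is found unacceptable, and the primary reason for poor fit recorded". Section 7.1 adds that "ID numbers will not be reused in event of screen failure or discontinuation". Section 10.1 says: "In the event of missing data, individual data points will be excluded in the analysis and not extrapolated from the collected data".

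**The concern.** Pairing cancels what a subject's two eyes share. It does not cancel a systematic difference between right and left eyes, such as might arise from measurement order or from handedness at insertion. If the two allocation groups are equal in size, such a difference averages out of the lens estimate but stays in the error variance, so the interval is wider than necessary and the test is conservative. If the groups are unequal, the difference also shifts the plain estimate for that split.

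Precision matters here because the hypothesis is equivalence and there are only about 30 pairs. The measured part of the primary variable, lens fit, could benefit, and the information needed is already collected.

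**Working it through.** The plan gives no power, SD, effect size or margin in the visible text, so there is no figure to reproduce.

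**Inputs.** From the documents: n = 30 pairs (section 7.1, approximate), alpha 0.05 (section 10.1), and the eye as the randomized factor (sections 3 and 7.2.1). Assumed: two-sided testing, no multiplicity adjustment (section 10.1 promises one but does not specify it), continuous outcomes, the OD:OS split n1:n2, and the OD-OS effect e. The unit of e is the residual SD of the test-minus-control difference D after eye is removed. It is not the raw SD of D, which e itself inflates.

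**Model.** D has mean (lens effect + e) when the test lens is in OD and (lens effect - e) when it is in OS. With allocation coded +1/2 and -1/2, the intercept is the average of the two group means, and the slope is 2e.

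**Formulas**, in residual SD units:
- Plain half-width: t(29) × sqrt{[1 + e² × (4·n1·n2/n²) × n/(n-1)] / n}, with t(29) = 2.0452.
- Half-width with the eye term: t(28) × sqrt{(1/n1 + 1/n2)/4}, with t(28) = 2.0484.
- Shift of the plain estimate for a given split: e × (n1 - n2)/n.

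**Worked case, 15:15, e = 0.5.** The plain variance factor is 1 + 0.25 × 30/29 = 1.2586, with square root 1.1219. The ratio is (2.0484/2.0452)/1.1219 = 0.893, an interval 11% narrower.

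Ratio of CI width, eye term to plain:

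| Split | e = 0 | 0.1 | 0.2 | 0.3 | 0.5 | Break-even e |
|---|---|---|---|---|---|---|
| 15:15 | 1.002 | 0.996 | 0.981 | 0.958 | 0.893 | 0.05 |
| 18:12 | 1.022 | 1.017 | 1.002 | 0.979 | 0.915 | 0.21 |
| 20:10 | 1.062 | 1.057 | 1.043 | 1.021 | 0.958 | 0.37 |

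**Shift of the plain estimate.** At 18:12 it is 0.3 × 6/30 = 0.06 SD for e = 0.3 and 0.5 × 6/30 = 0.10 SD for e = 0.5. At 15:15 it is zero.

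**Null rejection by simulation, nominal 5%.**
- Eye allocated by simple randomization, averaged over splits: the plain test stays at about 5% whatever the value of e.
- Given 15:15 and e = 0.5: about 3% for the plain test (conservative).
- Given 20:10: about 7% at e = 0.3 and 10% at e = 0.5 for the plain test.
- With the eye term: about 5% throughout.

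**How likely are uneven splits?** If allocation were simple 1:1 randomization of 30, which the documents do not state, the chance of 18:12 or worse would be 0.36 and of 20:10 or worse 0.10. A balanced schedule that lost three subjects from one group would give 15:12, where the eye term costs 0.8% at e = 0.

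**Visit 0 adjustment, slit lamp only.** Regressing the 6-hour difference on the Visit 0 between-eye difference multiplies the variance by (1 - r²) × 28/27, where r is the correlation of the between-eye differences. The factor is 1.037, 0.944 and 0.778 at r = 0, 0.3 and 0.5. After the change in t, the CI ratios are 1.020, 0.973 and 0.883, and break-even is about r = 0.2. Because clear corneas are an inclusion criterion, many Visit 0 grades may be zero in both eyes, and r may then fall below break-even.

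**The case against.** The strongest case is that nothing is wrong. A paired t test is a standard, valid analysis of a randomized contralateral comparison, and adding a covariate is a matter of preference. The benefit depends on an OD-OS effect that the documents give no reason to expect. At e = 0.1 and 15:15 the gain is only 0.4%, and the 11% needs e = 0.5. At uneven splits a small eye effect makes the adjusted interval wider: 4.3% at 20:10 with e = 0.2. Section 10.1 specifies neither a CI nor a margin, so no decision can be shown to change, and section 11.1 calls this a short feasibility study. All of this stands, and it is why the point is minor.

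A reader might infer from the 7% and 10% rejection rates that the planned test inflates type I error. The documents do not support that. Those rates hold only given a 20:10 split, and only with a sizeable eye effect. The split is not shown, the schedule may well be balanced, and no dropout rate is given. The absence of the Appendix 1 table from the public copy is not evidence of imbalance.

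A reader might also infer that slit lamp ought to be adjusted for Visit 0 grades. The gain there may be nil, so that step is optional.

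What survives is the asymmetry at a balanced split: the eye term costs 0.2% of CI width if useless and saves 2% to 11% at effects of 0.2 to 0.5.

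**Conclusion.** This is a minor, inexpensive improvement, not an error. The planned test is valid with respect to the omitted eye term. Using the randomized eye protects the lens estimate against an OD-OS difference: at 15:15 it changes CI width by +0.2%, -2% and -11% at e = 0, 0.2 and 0.5, and at an uneven split it also removes the shift. With no eye effect the cost is +0.2%, +2% and +6% at 15:15, 18:12 and 20:10.

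These sizes rest on 30 complete pairs, two-sided 5% testing, continuous outcomes and assumed values of e and the split. They are approximate for coarse 0-4 grades. The conclusion covers the measured part of the primary variable only; neither term applies to lens fit preference or to slow/medium/fast ratings. It says nothing about whether a difference test can support an equivalence claim, which is a separate question.

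**What to change.** Add two or three sentences to section 10.1, fixed before unmasking:

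1. For lens fit measures in mm and %, and other outcomes analysed as continuous (including slit-lamp grades if they are compared by t test), regress the test-minus-control difference on OD/OS allocation (+1/2 if the test lens is in OD, -1/2 if in OS). Report the intercept and its CI as the lens effect.
2. Report the OD:OS split analysed for each outcome, since exits and dropped points can change it.
3. Keep the plain paired t test as a sensitivity analysis.
4. Optional, slit lamp only: also include the Visit 0 test-minus-control difference. This is worthwhile only if the correlation of between-eye differences is expected to exceed about 0.2. If Visit 0 carries no information, it costs about 2% of CI width. Any rule for omitting it where few pairs differ at Visit 0 should depend on Visit 0 grades alone.

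The cost is a few lines of code and one degree of freedom per term, plus the CI widening given in the verdict if there is no eye effect. No new data or visits are needed.
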